#### **3.4.4.2 Drug Accountability**

The investigator will maintain accurate records of receipt of all drug supplies used in this study including lot numbers (if applicable) and dates of receipt. In addition, accurate records

will be kept regarding when and how much drug is dispensed and used by each subject in the study. Reasons for departure from the expected dispensing regimen must also be recorded. At the completion of the study, to satisfy regulatory requirements regarding drug accountability, all drugs will be reconciled and retained or destroyed according to applicable regulations.

### **3.4.5 Blinding**

This is a double-blind study. Neither the subjects nor the investigator will be aware of the treatment assignment. Blinding will be maintained throughout the study by use of active and placebo dose forms prepared to be similar in appearance. To maintain the blind, only designated pharmacy staff at the study site will have access to the randomization code and will prepare each dose for each subject. In order to prepare preliminary summaries of safety, PK, and/or PD data, as needed, to make timely decisions concerning adjustment of study procedures, dosing regimens, or potentially early termination of the study, certain designated staff at PhaseBio (e.g. study director, a single biostatistician, and bioanalytical scientist[s]) study drug accountability monitor, will receive unblinded data after each cohort completes Day 3 assessments. Except as noted above, all other members of PhaseBio will remain blinded. Access to the randomization code will be strictly controlled according to PPD SOPs.

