This initial cohort (Cohort 1) will include approximately 8 subjects ages 50 to 80 years pretreated with ASA + ticagrelor who will be randomized to 18 grams (g) of PB2452 or matching placebo administered as an initial 6 g bolus infused over 10 minutes, followed by 12 g infused over the next 15 hours and 50 minutes to complete a 16 hour administration regimen. This initial regimen was shown to be safe and well tolerated in healthy young adults (18 to 50 years) in a prior Phase 1 study and provided immediate and sustained reversal of the antiplatelet effects of ticagrelor. Following completion of Cohort 1, subsequent cohort(s) may test the same, higher, or lower dose levels, and/or different infusion regimens of PB2452 or matching placebo in the same population as in Cohort 1 or in different populations, such as, elderly subjects (65 to 80 years old) as determined by the Sponsor after examination of available PD and safety data from the prior cohort(s). A written Dosing Memo provided by the Sponsor to the clinical site will describe details of the dosing regimen, cohort population, cohort size, sampling schedules, and other cohort-specific study activities prior to initiation of each cohort. The maximum total dose of PB2452 administered to any subject will not exceed 30g. Duration of study drug infusions will not exceed 48 hours. The maximum administration rate of PB2452 will not exceed 18g over 30 minutes.

A SRC will review all available safety data from ongoing or completed cohorts and will document their review and assessment in written SRC minutes prior to initiation of a subsequent cohort. Dose escalation may occur only if the SRC affirms the dose and regimen from the previously completed cohorts were safe and well tolerated and no DLTs were observed.

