### **3.4.2.1 Dose Escalation**

The SRC will conduct a blinded review of all safety and tolerability data from a cohort at least through Day 3 (e.g., clinical laboratory results, AEs, ECGs, Holter monitoring reports if available, vital signs, and available PK data) and available data for each completed dose cohort and will document their review and assessment in written SRC minutes prior to initiation of a subsequent cohort. Dose escalation may occur only if the SRC affirms the dose and regimen from the previously completed cohorts were safe and well tolerated and no DLTs were observed.

The SRC will be minimally composed of the on-site PPD investigator/medical monitor, PhaseBio medical monitor, and PhaseBio clinical operations lead. Changes to the administration regimen (rate and duration) without escalation of the total dose or without

increases in the infusion rate will not require formal SRC approval. Similarly, reductions in the total dose or the infusion rate will not require SRC approval.

The investigator may make a recommendation concerning whether the safety profile is sufficient to proceed to a higher dose level, whether a pause in dosing for review of additional safety and/or PK data is needed, or whether adjustment of the dose of the next dose cohort is needed. The decision to adjust or pause the dose or proceed to the next cohort will be made by the SRC.

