### **3.4.7 Breaking the Blind**

A subject may be unblinded in the event of a DLT, an SAE, or if there is a medical emergency when the identity of the drug must be known to properly treat a subject. A cohort may be unblinded to determine if dose escalation to the next dose level will or will not proceed. In the event of a medical emergency requiring identification of the study drug administered to an individual subject, the investigator will make every attempt to contact the medical monitor to explain the need for opening the code within 24 hours of performing that task. The investigator will be responsible for documenting the time, date, reason for the code break, and the names of the personnel involved.

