### **3.6.5 Interim Analyses**

There is no interim analysis planned for this study.

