Following completion of Cohort 3, subsequent cohort(s) may have been enrolled to test the same, higher or lower dose levels, and/or different infusion regimens of PB2452 or matching placebo in the same population as in Cohort 3, or in different populations such as elderly subjects (65 to 80 years old), as determined by the Sponsor after examination of available PD and safety data from the prior cohort(s) and described in a subsequent Dosing Memo. Duration of study drug infusions will not exceed 48 hours. No cohort was enrolled following Cohort 3.

A Safety Review Committee (SRC) reviewed all available safety data from ongoing or completed cohorts and documented their review and assessment in written SRC minutes prior to initiation of a subsequent cohort. Dose escalation would occur only if the SRC affirms the dose

and regimen from the previously completed cohorts were safe and well tolerated and no dose-limiting toxicities (DLTs) were observed.

The study consisted of a Screening period (Days -45 to -4), a Check-in day (Day -3), a 48 hour Pretreatment Period starting on Day -2, an on-site Randomization/Treatment day (Day 1), 3 days on-site for treatment and safety monitoring, a Follow-up Visit (Day 7), and a Final Follow-up visit (Day 28 [± 2 days]). Two days prior to Randomization (Day -2), subjects were administered ticagrelor 180 mg orally twice daily (BID) until the final dose on the morning of Day 1 before receiving study drug. The first ticagrelor 180 mg oral dose was administered on the morning of Day -2 followed by 180 mg every 12 hours until the 5th dose was administered on the morning of Day 1.

Subjects checked in to the clinical site (PPD) on Day -3. In the morning on Day -2, subjects began pretreatment with ticagrelor as described in the preceding paragraph. On Day 1, subjects who meet all the inclusion criteria and none of the exclusion criteria were randomized in a ratio 3:1 (PB2452:placebo), to receive an IV dose of PB2452 or placebo 2 hours following the 5th ticagrelor dose. Subjects may have been discharged from the clinical site between Days 3 and 7 inclusive to return for a Follow-up visit on Day 7, if already discharged, and on Day 28 (± 2 days).

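### The plan says there is no interim analysis, yet sponsor staff receive unblinded data after each cohort, and the SAP, written after enrolment, changes the PRU parameters without saying so

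*Protocol*

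**What the plan says.** Protocol 3.6.5 (both Parts) and SAP 12 carry the same sentence: "There is no interim analysis planned for this study".

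Protocol 3.4.5 (both Parts) and SAP 4.2 describe how comparative data reach the sponsor during the study. Designated sponsor staff "will receive unblinded data after each cohort completes Day 3 assessments". The examples given are the study director, a single biostatistician, bioanalytical scientists and the drug accountability monitor. The material is safety, PK and/or PD summaries, prepared where needed, and the purpose is "to make timely decisions concerning adjustment of study procedures, dosing regimens, or potentially early termination of the study". The rest of the sponsor stays blinded (protocol 3.4.5), and SAP 4.2 places general unblinding after hard lock.

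Protocol 3.1 (both Parts) leaves later regimens to the sponsor, once it has examined PD and safety data from earlier cohorts. For the Safety Review Committee (SRC), protocol 3.4.2.1 states: "The SRC will conduct a blinded review of all safety and tolerability data from a cohort at least through Day 3". Protocol 3.4.7 adds: "A cohort may be unblinded to determine if dose escalation to the next dose level will or will not proceed". Under 3.4.2.1, regimen changes that raise neither the total dose nor the infusion rate need no formal SRC approval.

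The SAP describes enrolment in the past tense: two cohorts in Part A and one in Part B (SAP 3.3), and "No cohort was enrolled following Cohort 3" (SAP 3.1). SAP 13 states that the SAP makes no change from the protocol.

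**The concern.** Summaries by arm, reviewed between cohorts in order to change the regimen or end the study, are interim reviews in substance, whatever they are called. A plan that provides for them in one section and says in another that there is no interim analysis gives the report no place to record which reviews took place, when, and what they decided.

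This matters more because the SAP text is late and its PRU parameters are not the protocol's. Reversal measured by PRU against placebo is one of the two primary objectives in each Part. If the list of PRU results was settled when some sponsor staff may already have known PRU by arm, and the SAP also says that nothing changed, a reader cannot separate results fixed in advance from results chosen later. What is at stake is pre-specification and how the PD results are read. No error rate is involved.

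**Working it through.** The documents state no alpha, power or effect size here, so there is no figure to reproduce. The check is a comparison of texts plus simple counts.

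**1. Number of possible reviews.** The ceilings are 5 cohorts (Part A) and 3 (Part B): 5 + 3 = 8. Enrolled were 2 + 1 = 3. Up to three releases may therefore have occurred; the documents do not record how many did. In a cohort of 8 to 12 at 3:1, a release covers 8 × 3/4 = 6 to 12 × 3/4 = 9 subjects on PB2452 and 8 × 1/4 = 2 to 12 × 1/4 = 3 on placebo.

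**2. Timing of the SAP text.** The statement that no cohort followed Cohort 3 can only have been written once enrolment had ended. Cohorts 1 and 2 are Part A, and Cohort 3 opens Part B. If the planned releases took place, arm-level data from Cohorts 1 and 2 were with some sponsor staff before this text was written. Whether a Cohort 3 release also came first is not stated.

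**3. PRU parameters side by side.** Protocol 2.2.2 (the same list in both Parts) against SAP 3.2.3 and 11.2:

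| Protocol | SAP |
|---|---|
| Minimum % inhibition within 4 h | Absent |
| PRU AUC over the first 4 h | Absent |
| Proportion with PRU ≥180 within 4 h | Time to ≥180 listed; proportion not listed |
| Proportion at ≥60, ≥80 and 100% of baseline within 4 h | Proportion at 60, 80 and 90%, within 30 min or 4 h |
| Time to 60, 80 and 100% within 4 h | Time to 60, 80 and 90%; no 4 h limit stated |
| Duration of 80% and 100% response | Absent |
| Not listed | Times to PRU 200 and 220; maximum PRU, time to it, and maximum within 4 h; maximum % of baseline |

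Of six protocol items, three are absent, two exchange 100% for 90%, and one appears only in another form. SAP 13 lists none of this.

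**4. Whether the missing items can still be produced.** They need no new data. SAP 11.1 gives draws at 5 minutes and at 0.25, 0.5, 1, 2 and 4 hours, then out to 48 hours. Minimum % inhibition within 4 h equals 100 × (1 − maximum PRU within 4 h ÷ baseline PRU), with the protocol's pre-ticagrelor baseline, and the SAP already computes that maximum. AUC, duration and the PRU ≥180 proportion come from the same series.

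**5. Whether the protocol list predates the releases.** SAP section 1 cites Part A Final 2.0 and Part B Final 1.0, both dated 29 July 2019. The Part B synopsis already describes Part A in the past tense. The dates of the releases, and of the version that first set each PRU parameter, are not given. The protocol list is the earlier of the two lists, but the documents do not establish that it came before every release.

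**The case against.** The strongest reply is that nothing is hidden. Recipients, timing, type of data and purpose are stated in protocol 3.4.5 (both Parts) and again in SAP 4.2, and protocol 3.1 says openly that the sponsor chooses later regimens after seeing PD and safety data. Choosing regimens between cohorts is the design of a sequential-cohort study. This reply stands: a reader might infer concealed looks, and the documents contradict that. What is missing is identification of the reviews as interim reviews and a record of them.

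A reader might also infer that the SAP's PRU definitions were chosen because of the unblinded data. The documents show only the order in time. Summaries are prepared where needed, access is limited to designated staff with a single biostatistician, and no section says who wrote the SAP or why the parameters changed. The protocol also allows additional PD parameters. That covers the additions, but neither the omissions nor a statement that nothing changed.

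A third inference is that the study stopped at three cohorts because of what was seen. The numbers 5 and 3 are ceilings, and no section says that the study ended early or why.

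Finally, one might claim inflated type I error. The sample is not powered, Part A PD analyses are descriptive, and in Part B any comparison of arms is optional and is to be read as descriptive. No alpha or stopping boundary exists, so none is spent.

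**Conclusion.** The conflict is real and appears in both Parts of the protocol and in the SAP. Reviews of unblinded data that may change the regimen or end the study are planned, disclosed, and not identified as interim review. Separately, a SAP written after enrolment of all three cohorts alters every PRU item in the protocol's list while declaring no change.

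The size is documentary: up to three releases may have occurred, and all six protocol PRU items are dropped, altered or recast. No bias in a result can be calculated from the documents. The conclusion does not depend on the SAP authors having been unblinded. It rests on the wording of the sections, on the past tense of the SAP, and on the status of PRU as a primary objective.

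Relabelling SAP 12 alone would change no result. Reporting the protocol-defined parameters, and marking the others as later additions, does change what the trial can be said to have pre-specified. The change is worth making.

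**What to change.** All changes belong in the SAP. Enrolment is complete, and amending protocol 3.6.5 would need submission to the IRB for little gain.

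1. In SAP 3.2.3 and 11.2, report the protocol-defined PRU parameters as the pre-specified PD results: minimum % inhibition within 4 h, 4-hour AUC, proportion with PRU ≥180, proportions at and times to 60, 80 and 100% response, and duration. Label the SAP-only parameters and thresholds as added after enrolment.
2. In SAP 13, replace the no-change statement with a list of these differences.
3. Replace SAP 12 with a statement, cross-referring to 4.2, that unblinded post-cohort reviews informed regimen and termination decisions. Give the date of each review that took place, the date of the SAP, and the date of the protocol version that first set each PRU parameter. State whether the unblinded biostatistician set the definitions. If a protocol parameter proves to be later than a review, say so beside it.

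The cost is a few extra PD tables from data already collected, some footnotes, and a post hoc label on some results.

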### **3.4.6 Treatment Compliance**

All doses of study drug, matching placebo, and ticagrelor will be administered at the clinical site under direct observation of clinic personnel and recorded in the eCRF.

The date, time, and actual dose received of study drug and matching placebo infusion and ticagrelor dosing will be recorded on the appropriate pages of the eCRF. If a subject was scheduled to receive any of these drugs and did not, the reason for the missed or partial dose will be recorded in the eCRF pages.

### **3.4.7 Breaking the Blind**

A subject may be unblinded in the event of a DLT, an SAE, or if there is a medical emergency when the identity of the drug must be known to properly treat a subject. A cohort may be unblinded to determine if dose escalation to the next dose level will or will not proceed. In the event of a medical emergency requiring identification of the study drug administered to an individual subject, the investigator will make every attempt to contact the medical monitor to explain the need for opening the code within 24 hours of performing that task. The investigator will be responsible for documenting the time, date, reason for the code break, and the names of the personnel involved.

### **3.4.8 Prior and Concomitant Medication**

Prior medications are defined as medications taken prior to the first dose of study medication, regardless of whether they are continued or not after the first dose of study medication.

Concomitant medications are defined as medications taken on or after the first dose date of study medication, including those started before the first dose and continued into the treatment period.

#### **3.4.8.1 Prior Medication and Therapies**

Information about prior medications taken by the subject within 30 days before he or she provides informed consent will be recorded in the subject's eCRF.

#### **3.4.8.2 Concomitant Medication and Therapies**

Subjects are prohibited from taking any additional prescription or OTC medications or nutritional supplements during their participation in the study (with the exception of protocol allowed medications, hormonal birth control and/or chronic medications).

Paracetamol/acetaminophen or other medications may be administered at the discretion of the investigator at doses of up to 2 g/day.

Subjects are prohibited from therapy with strong CYP3A inhibitors, CYP3A substrates with narrow therapeutic indices, or strong CYP3A inducers. A list of example inhibitors and inducers of CYP3A4 is presented in [Appendix 7.2](#).

Subjects are prohibited from taking NSAIDs (within 14 days of screening), anticoagulants, or other antiplatelet agents within 30 days of screening.

Concomitant medications will be coded using the latest version of the World Health Organization Drug Dictionary (WHO-DD). With the exception of drug therapy specified in the protocol, if drug therapy is taken, a joint decision will be made by the investigator and the Sponsor whether to continue or discontinue the subject based on the time the medication was administered, its pharmacology and PK, and whether the use of the medication will compromise the subject's safety or interpretation of the data. It is the investigator's responsibility to ensure that details regarding the medication are accurately recorded in the eCRF.

## **3.5 STUDY PROCEDURES**

After signing the ICF, subjects will have study procedures at the time points specified in the Schedule of Events ([Appendix 7.1](#)).

### **Screening (Days -45 to -4)**

- Subjects sign informed consent
- Inclusion/Exclusion criteria

- Demographics
- Medical history
- Urine drug screen, including cotinine
- Urine alcohol screen
- Serum pregnancy test for women of childbearing potential
- Serology test
- Stool occult blood test
- Physical examination, full, including height, weight, and BMI calculation
- Vital signs measured including SBP and DBP, oral body temperature, respiration rate (RR), and HR
- 12-lead ECG
- Clinical laboratory tests including hematology, chemistry, coagulation, and urinalysis

#### **Screening (Day -7)**

- Subjects start receiving ASA 81mg QD (Subjects who enter the study already taking ASA daily will document a daily ASA 81 mg dose.)

#### **Screening (Day -6)**

- Subjects receive ASA 81mg QD

#### **Screening (Day -5)**

- Subjects receive ASA 81mg QD

#### **Screening (Day -4)**

- Subjects receive ASA 81mg QD

#### **Check-in/Pretreatment - Baseline (Day -3)**

- Subjects receive ASA 81mg QD
- Inclusion/Exclusion criteria
- Urine drug screen, including cotinine
- Urine alcohol screen
- Serum pregnancy test for women of childbearing potential
- Admission to study site
- Physical examination, full, including weight,
- Vital signs measured including SBP and DBP, oral body temperature, RR, and HR
- Clinical laboratory tests including hematology, chemistry, coagulation, and urinalysis
- Blood sampling for PD (LTA/PRU/VASP)
- Serum immunogenicity
- AEs collected

#### **Pretreatment - Baseline (Day -2)**

- Subjects receive ASA 81mg QD

- Administration of ticagrelor begins in the morning, single dose oral ticagrelor 180 mg (2 x 90 mg), followed by oral ticagrelor 90 mg every 12 hours for 4 additional doses through to Day 1 (2 hours before study drug is initiated; for a total of 5 doses of ticagrelor)
- Urine sampling, PK
- Blood sampling for PD (LTA/PRU/VASP)
- AEs collected

### **Pretreatment - Baseline (Day -1)**

- Inclusion/Exclusion criteria
- Subjects receive ASA 81mg QD
- 12-lead ECG
- Biomarkers
- Ticagrelor administered
- Clinical laboratory tests including hematology, chemistry, coagulation, and urinalysis
- AEs collected

### **On-site Treatment – Randomization (Day 1)**

- Administration of ASA 81mg 2 hours prior to study drug administration
- Administration of ticagrelor 2 hours prior to study drug administration
- 12-lead ECG *before* study drug is administered
- Continuous 12-lead Holter monitor placed 2 hours *before* administration of study drug will remain in place for 24 hours *after* initiation of study drug. Subjects should be resting in the supine or semi-recumbent position depending upon Dosing Memo.
- Vital signs (SBP, DBP, oral body temperature, RR, HR) measured 30 to 60 minutes prior to and during infusion of study drug according to Schedule of Events ([Appendix 7.1](#))
- Randomization
- Administration of PB2452 or matching placebo at Hour 0
- Blood sampling for PK: plasma PB2452, ticagrelor, and TAM PK, collected within 10 minutes *before* initiation of PB2452 infusion at Hour 0
- Blood sampling for PK: plasma PB2452, ticagrelor, and TAM PK, collected according to the cohort-specific Dosing Memo
- Blood sampling for PD: LTA/PRU/VASP according to the cohort-specific Dosing Memo
- Urine sampling (PK)
- Infusion site assessment
- Serum immunogenicity prior to dosing
- AEs collected

### **On-site Treatment (Day 2)**

- Vital signs measured
- 12-lead ECG
- Continuous ECG recording (Holter) for ECG evaluation to remain in place for 24 hours *after* initiation of study drug on Day 1
- Administration of ticagrelor in cohorts specifying a 6th dose of ticagrelor
- Blood sampling for plasma PB2452, ticagrelor, and TAM PK, collected according to the cohort-specific Dosing Memo
- PK Urine sampling
- Blood sampling for PD: LTA/PRU/VASP according to the cohort-specific Dosing Memo
- Biomarkers
- Infusion site assessment
- Clinical laboratory tests including hematology, chemistry, coagulation, and urinalysis
- AEs collected

